4. OBJECTIVES*

We propose to prospectively randomize orthopedists, with their patients, to receive (or not) a real-time, web-based system intervention: the OA Care plan. The OA Care plan will include individualized, patient-centric information: (1) trended patient-reported OA pain and function, (2) tailored estimates of likely TJR benefits and risks based on a contemporary US cohort of 25,000 TJR patients (FORCE-TJR Registry), (3) evidence-based information for non-operative care, and (4) individual patient goals.

Specific Aims include:

Aim 1. Patients and their Caregivers/Trusted Others will refine the design, content, and usability of a real-time, web-based individual OA Care plan to guide TJR and non-operative OA care decisions.

Aim 2. Randomize 40 orthopedists, and their patients, to receive the OA Care plan at the time of orthopedic consultation (intervention) vs. usual care (control) and compare (a) OA care decision process and quality and (b) quality of OA care as measured by pain relief and functional gain in the two arms at 6 and 12 months after the decision, and assess the impact of decision quality on quality of OA care.

Aim 3. Randomize 36-40 orthopedists, and their patients, to receive the OA Care plan plus peer, family, and primary care physician support (OA Care plan+Support; intervention called A.S.K. Coaching) vs. the OA Care plan alone and compare the quality of OA care decision and quality of care (pain relief, functional gain) in the two arms.

When moving the PCORI contract to Northwestern in early 2019, we revised the sample size estimates required to meet the same study power and analytic plan for both Aim 2 and Aim 3. Using the early study data, we determined that n=3000 patients in Aim 2 and n=3000 patients in Aim 3 was adequate to meet statistical goals. We also determined that fewer surgeons (N= 36-40) would be required in Aim 3 to consent 3000 patients. PCORI agreed to the changes in number of surgeons and patients. We clarified this change in the ISP.

Based on the components of the Chronic Care Model, this technology-delivered, individualized OA Care plan will enable patients and clinicians to make treatment decisions based on patient symptoms, goals, and comparative effectiveness evidence. We hypothesize that OA Care plan users, as compared to usual care, will report greater decision quality for both TJR or non-

INVESTIGATOR STUDY PLAN

12.14.2021

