If the Research Coordinator is unable to reach the potential participant by phone, the Final contact Recruitment and Follow-up-e-mail-snail mail 2-14-18 letter will be sent to the patient either by email or snail mail (see attached). This letter will also be used if consented participants do not return follow-up surveys.

Surgeon offices will be randomized to Usual Care or Intervention sites. During Aim 2, after completing the surveys in the clinic, usual care patients and surgeons will have the ability to see PRO scores, but will NOT receive feedback (no OA Care Plan). This is the current standard of care in orthopedic clinics. For intervention sites, the patient and surgeon will receive the OA Care Plan (named the A.S.K. Report).

INVESTIGATOR STUDY PLAN

12.14.2021

The DCC will follow-up with patients at 3 time points: 1-month Decisional Conflict Scale and Shared Decision Making Process Survey; 6 months and 12 months after surgery or decision to use non-surgical method of managing OA. (see 1-month Decisional Conflict Scale, 6 and 12-month [Knee/Hip] surveys attached). Surveys will be mailed and/or emailed based on participant preference. The 12 month surveys are standard clinical care; the 1 month, and 6 month contact are for the research. After receiving IRB approval (hopefully September 2020), newly enrolled patients will also respond to Covid-19 measures via the same web-based data capture system used in the rest of the study at 1-month, 6 months and 12 months.

Participants will receive a \$20 gift card after completing the 1-month Decisional Conflict Scale for their time

During Aim 3, Usual Care sites will receive the OA Care Plan (A.S.K. Report), and Intervention sites will receive the Enhanced OA Care Plan, including access to Patient Peer Support website and PCP reports. All surgeons that used the OA Care plan in Aim 2 will be invited to participate in the Enhanced OA Care plan in Aim 3.

When patients are contacted to complete the post-visit 1-month Decisional Conflict Scale, we will inquire as to whether the surgeon and patient reviewed the A.S.K. Report together. This allows us to understand report use rates for all patients.

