12. DATA AND SPECIMEN BANKING*

No specimens will be banked for future use. See #13, Data Management, for data retention and access.

13. Data Analysis and Management*

Responsibility for 6 month and 12 month outcome data collection was transferred from UMMS to Northwestern during 2021. At the completion of study enrollment (on or about March 1, 2022), the UMMS data enrollment and collection services will be completed. At that date, the UMMS data center will have already, or will then, transfer all enrollment, patient-reported, and study data to Northwestern for the analytic team to manage and analyze. The UMMS data center will confirm that they expunged all ASK study data from the web-based data capture systems (DatStat, RedCap) and UMMS data storage files within UMMS.

Aim 1

We will transcribe recorded interviews and code using content analysis techniques to identify themes. We expect to achieve data saturation at or before completing 30 interviews with patients and 30 with caregivers.

AIM 2 and 3. Sample size and effect size estimates:

The trial is designed with $\geq 80\%$ statistical power at 5% significance level to detect intervention effects that are meaningful to both patients and surgeons, and health systems. In total, 40 (Aim 2) or 54 (Aim 3) surgeons will be randomized equally to treatment and control arms with an average of 100 patients/surgeon. Based on data from FORCE-TJR, the intraclass correlation within surgeon is approximately 0.02. Using two independent group t-tests adjusting for within surgeon clustering, the trial can detect an intervention effect of (a) improved decision quality of >0.16 SD ; (b) improved quality of OA care defined in two ways: 6 month post-decision pain relief (KOOS/HOOS) of ≥ 3.3 points for TKR patients (34.1 vs. 37.4; SD=20.8) and ≥ 3.3 for THR patients (45.7 vs. 49.0; SD=20.9) or greater proportion of patients with meaningful pain relief (17 points in HOOS/KOOS pain score) of $\geq 6.1\%$ more TKR patients (77.9% vs. 84.0%) and $\geq 4.2\%$ more THR patients (90% vs. 94.2%).

Aims 2 and 3: Overview of analytic approach. We hypothesize (Aim 2) that patient/clinician use of the OA Careplan will improve decision quality as well as

INVESTIGATOR STUDY PLAN

12.14.2021

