Aim 3: To evaluate the effect of the OA Careplan+Support (Coaching) on (a) decision quality and (b) pre-to-post decision pain relief and functional gain, we will do the following. The 20 surgeons (and their patients) who received usual care in Aim 2 will receive the OA Careplan intervention (n=2,000) in Aim 3. The 20 surgeons who received the OA Careplan in Aim 2 will now receive the OA Careplan+Support (n=2,000 new patients) in Aim 3. Additional surgeons will be recruited and randomized to the 2 arms. First, we will compare patient characteristics between users and non-users of the SUPPORT. We will then identify patient as well as site/surgeon determinants of the use of the SUPPORT using multi-level logistic regression models, and estimate individual patient's probability (propensity) for any use of SUPPORT strategies. Because use of the SUPPORT is not randomized, we will use inverse propensity weighting approach to estimate the effects of the SUPPORT on outcomes (decision quality, pain, function).

We will begin with descriptive analysis, and estimation of crude OA Careplan+Support intervention effects, overall and by select patient subgroups. We will further use GLLAMM to estimate covariate---adjusted intervention effects, overall and by patient

INVESTIGATOR STUDY PLAN

12.14.2021

subgroup, and adjust for propensity scores, plausible surgeon and patient factors. Statistically significant differences between the two arms indicate possible incremental SUPPORT intervention effect beyond the OA Careplan alone. We will conduct pre-post comparisons of the outcomes (decision quality, pain relief) for patients of the 20 surgeons who were in the OA Careplan intervention arm in Aim 2 and are now in the OA Careplan+Support arm.

Statistically significant pre-post changes in outcomes support possible incremental effects of the SUPPORT intervention. We will derive a usage score of the SUPPORT system (e.g., frequency and duration of use) as an indicator of “dosage” of use and use it to estimate a possible “dose-response” relationship between level of use and patient outcomes in the GLLAMM. We will also identify relevant patient-and site/surgeon predictors of any and higher levels of usage.

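### For surgeons carried over from Aim 2, the Aim 3 contrast mixes Support with having already received the report, and the sections disagree on how Aim 3 surgeons were allocated

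*Combined protocol and SAP*

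**What the plan says.** The allocation of Aim 3 surgeons is described in two ways.

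- **Step-up from the Aim 2 arm.** Section 13, Aim 3 paragraph: "The 20 surgeons (and their patients) who received usual care in Aim 2 will receive the OA Careplan intervention" and "The 20 surgeons who received the OA Careplan in Aim 2 will now receive the OA Careplan+Support". Randomisation is mentioned there only for newcomers: "Additional surgeons will be recruited and randomized to the 2 arms". Their number is not given. Section 8 agrees on the step-up: "All surgeons that used the OA Care plan in Aim 2 will be invited to participate in the Enhanced OA Care plan in Aim 3". It also says that Aim 2 usual-care surgeons could see PRO scores but had no Care plan.
- **Randomisation in Aim 3.** Section 4: "Aim 3. Randomize 36-40 orthopedists, and their patients, to receive the OA Care plan plus peer, family, and primary care physician support". The sample-size paragraph of Section 13: "40 (Aim 2) or 54 (Aim 3) surgeons will be randomized equally to treatment and control arms". Section 6 (patient interview criteria) and the Aim 3 procedures in Section 8 also call the Aim 3 sites or surgeons randomised.

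On interpretation, Section 13 states: "Statistically significant differences between the two arms indicate possible incremental SUPPORT intervention effect beyond the OA Careplan alone". The candidate surgeon covariates named there are volume, procedure type and region, kept or dropped on a p<0.10 screen. The pooled analysis of both phases names a three-level intervention indicator, but no phase term and no term for earlier receipt of the report.

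**The concern.** If the step-up was followed, carried-over Support surgeons differ from carried-over control surgeons in two respects: they are offered Support, and they were given the report in Aim 2. Nothing within that group can separate the two. An Aim 3 difference in decision quality, pain or function could then come from surgeons already familiar with the report, with Support adding little. It could also hide a Support effect, if earlier receipt works the other way. The question for Aim 3 is what Support adds to the report, and this contrast does not isolate that.

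The disagreement between sections matters as well. If all surgeons were re-randomised, the aliasing goes away and the Section 13 text is wrong. If they were not, the other sections do not tell the reader that most or all Aim 3 allocations were inherited from Aim 2.

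**Working it through.** **Inputs.** All are from Section 13 unless noted: ICC 0.02; on average 100 patients per surgeon; 40 surgeons (Aim 2) or 54 (Aim 3); 5% significance level (two-sided assumed, since sidedness is not stated); at least 80% power; detectable decision-quality effect 0.16 SD. Section 4 gives 36–40 surgeons and 3,000 patients for Aim 3. The size of an experience effect is in no document; 0.05 and 0.10 SD are assumptions.

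**1. The plan's own figure.** Design effect = 1 + (100 − 1) × 0.02 = 2.98. With 20 surgeons per arm, effective n = 2,000 / 2.98 = 671 per arm. Detectable effect = (1.96 + 0.84) × √(2/671) = 0.153 SD, or 0.157 SD using t on 38 df. The stated 0.16 SD is reproduced.

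**2. Earlier receipt of the report, by Aim 3 arm.**

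| Scenario | Support | Careplan alone | Correlation with arm |
|---|---|---|---|
| 40 surgeons, all carried over | 20/20 | 0/20 | 1.0 |
| 54 surgeons, 54 − 40 = 14 new (7 per arm) | 20/27 (74%) | 0/27 | 0.77 |

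**3. Bias if Support does nothing.** Bias = (share exposed in Support − share exposed in control) × assumed experience effect.

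- All carried over: 1.0 × 0.05 = 0.05 and 1.0 × 0.10 = 0.10 SD. Divided by 0.16, these are 31% and 63%.
- 54 surgeons: 0.741 × 0.05 = 0.037 and 0.741 × 0.10 = 0.074 SD. Divided by 0.16, these are 23% and 46%.

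**4. Chance of a significant result with inert Support** (100 patients per surgeon).

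- 40 surgeons: SE = √(2/671) = 0.0546. The bias is 0.92 or 1.83 SE, so the chance is 15% or 45% instead of 5%.
- 54 surgeons: effective n = 2,700 / 2.98 = 906 per arm, SE = 0.0470. The bias is 0.79 or 1.58 SE, so the chance is 12% or 35%.

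**5. What can be separated** (54 surgeons, 100 patients each).

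- Unadjusted arm contrast: detectable effect 0.132 SD.
- Adding a prior-exposure term only: 0.205 SD. This borrows from a comparison of carried-over with new Support surgeons, which is not randomised.
- Adding prior exposure and a carried-over/new stratum: 0.259 SD. The Support estimate then comes from the new surgeons alone.
- New surgeons alone, 7 versus 7: effective n = 700 / 2.98 = 234.9 per arm, SE = 0.092, detectable effect 0.26 SD (z) or 0.28 SD (t, 12 df).
- The same with 3,000 patients over 54 surgeons (about 56 each): design effect 2.09, effective n = 186 per arm, SE = 0.104, detectable effect 0.29 SD (z) or 0.32 SD (t).
- No new surgeons: prior exposure and Support are the same variable, so no model separates them.

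**The case against.** The plan is hedged: it speaks of a possible increment. It also plans other analyses of Support: users against non-users with inverse propensity weighting, a dose-response model on usage, and a pre-post comparison in the 20 stepped-up surgeons. The first two vary Support use among patients who were offered it, so the between-arm gap in experience need not drive them. The covariate list is one of candidates and could be extended.

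These points are correct but do not repair the between-arm contrast. Use of Support is self-selected, and in the pre-post comparison experience and calendar time move together with Support. The hedge leaves Support as the only explanation offered.

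A reader might infer several stronger things that the documents do not support:

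- *That Aim 3 is not a randomised comparison.* Carried-over surgeons keep their Aim 2 randomisation, so the comparison of sequences is fair.
- *That Section 4 is the text in error.* Several sections say randomised, and the Aim 3 paragraph of Section 13 still carries 2,000 patients per arm against 3,000 in total in Section 4, so it may be the older text.
- *That Support surgeons had used the report for 1.5 years.* The documents say they received it. The 1.5 years is the recruitment period anticipated in Section 9, and the study itself asks whether the report was used.
- *That a decision-quality difference must reflect experience, because the Decisional Conflict Scale precedes the coaching invitation in Section 8.* That is a separate question of outcome timing. It does not show that an experience effect exists.

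**Conclusion.** The point holds, conditional on the step-up in Section 13 having been followed. The carried-over contrast is then a valid randomised comparison of two sequences: Careplan followed by Careplan+Support, against usual care followed by Careplan. It does not isolate Support, and the planned reading as an increment beyond the Careplan alone is not supported by it.

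The possible bias is 0.05–0.10 SD with no new surgeons and 0.037–0.074 SD with 14 new among 54. Both ranges rest on an assumed experience effect whose size and direction are unknown. New surgeons dilute the problem but do not remove it. Whether there are any is unclear: 54 surgeons implies 14, while 36–40 may imply few or none. If all surgeons were in fact re-randomised for Aim 3, the aliasing disappears and what remains is a text conflict to correct.

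**What to change.** 1. Reconcile the Aim 3 allocation in Sections 4, 6, 8 and 13. State the allocation actually used and the numbers of carried-over and newly randomised surgeons, settling 36–40 against 54.
2. If the step-up was followed, reword the interpretation: the carried-over contrast is Careplan+Support with surgeons previously given the report, versus Careplan with first-time recipients. Apply the same caution to the pooled three-level model.
3. If there are new surgeons, put both a prior-report-exposure term and a carried-over/new stratum term in the Aim 3 model, exempt from the p<0.10 screen. Report the new-surgeon contrast separately, with its limited precision.
4. If there are none, state that Support cannot be separated from prior exposure.

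No re-randomisation or new data are needed beyond each surgeon's Aim 2 arm. The cost is precision for the separated Support estimate (detectable effect about 0.26–0.32 SD against 0.16 SD) and a narrower headline claim.

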After the research coordinator completes the verbal consent process and the 1-month Decisional conflict assessment, s/he will then invite the patient to participate in the one-hour ASK Coaching session. (See attached Aim 3 additions to invitation phone call Coaching invitation). The coordinator will review the Coaching session Fact Sheet and answer questions. Participation in the Coaching session is not mandatory, but is encouraged as a way to review the information in the ASK report, and coach patients to use the information when discussing treatment options with their medical team. The session is 1 hour and uses a virtual Zoom web-platform. Participants can also opt to join by phone alone. Sessions will be scheduled weekly, alternating between mid-day and early evening to meet participant needs, and led by a trained health educator. The session will not offer clinical advice. (See Coaching session script and ASK Coaching Power-point slides.)

Participants scheduled to attend the Coaching session will receive a mailing with another copy of their ASK report to refer to during the session, and (1) a welcome letter, (2) a copy of the Coaching Powerpoint slides, (3) the “I have a voice” patient handout to prepare for medical visits, and (4) instructions for using the Zoom conferencing system. (See attachments – Coaching session welcome letter, ASK Coaching Powerpoint Slides, I Have a Voice patient handout, and Zoom Instructions).

At the end of the Coaching session, participants will be introduced to a study website that integrates for easy access publicly available patient information about managing arthritis. See attached ASK Website Outline, including both text and informational web-links as well as the ASK Annotate Report for Patients, which will be available on the site. The website links patients to professional society information (e.g., American Association of Orthopedic Surgeons, American Physical Therapy Association) and patient advocacy information (e.g., Arthritis Foundation).

After the Coaching session, participants will receive two emails and one postcard:

- (1) Sharing the link to the study website, and asking participants if they choose to share the ASK report with their primary care provider. If they choose to share it, participants will reply to the email granting permission and include the name and email address of the provider. If they choose not to share, they will do nothing.

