10. STUDY ENDPOINTS*

Primary Outcomes Measures:

1. To assess the effect of OA Careplan on (a) decision quality using a validated Decisional Conflict Scale and (b) pre-to-post decision pain relief and functional gain, using the HOOS (for hip patients) or KOOS (for knee patients).
2. To evaluate the effect of the OA Careplan+Support on (a) decision quality using Decisional Conflict Scale and (b) pre-to-post decision pain relief and functional gain, using the HOOS or KOOS.

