satisfaction with the OA care decision, as compared to usual care. Further, we hypothesize that improved decision quality will mediate quality of OA care as measured by lower pain and higher function at 6 and 12 months (KOOS/HOOS) after decision for both TJR and non-operative care. In Aim 3, we hypothesize that the OA Careplan+Support (vs. OA Careplan alone) will incrementally enhance decision quality and quality of OA care (for those who choose to use the Support) with the same measures used in Aim 2.

The general analytic approaches for Aims 2 and 3 are similar and summarized here. The underlying models extend our previous award-winning TKR outcome prediction model where discrete outcome sub-groups were identified. We will adhere to the intent-to-treat principle to analyze the trial data; the intervention status of the surgeon/site and their patients will be analyzed according to their status at the time of intervention. First, descriptive statistics for all relevant outcomes will be tabulated by treatment arm. Select patient factors (e.g., race, sex, function; comorbid factors) that may contribute to heterogeneity of treatment effects will be compared using univariate methods such as t-test for normally distributed variables, Wilcoxon rank sum test for skewed continuous variables, or Chi² test for categorical variables. We will examine distributions of outcomes, identify proper distribution assumptions, and determine whether or what types of transformations are indicated.

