Second, we will use GLLAMM to analyze the differences in joint pain and function at 6 and 12 months after the care decision between OA Careplan and comparison arms. We will pool data from both arms in the two phases. We will include an indicator variable to represent intervention status (usual care, OA Careplan, or OA Careplan+Support). We will assess whether 6 and 12 month pain differ between intervention arms. Next, we will repeat this process for the patients with meaningful (>17 point) change in HOOS/KOOS pain score. We expect pain relief will be significantly improved in the OA Careplan arm, with greater improvement to occur in the OA Careplan+Support, compared to the usual care group. Finally, we will formally test the mediation effects of Careplan and Careplan+Support on pain relief and functions at 6 and 12 months, using the two level structural equation models with mediation effects by Krull and MacKinnon (2001) and Preacher, Zyphur and Zhang (2010).

Only those listed in our IRB application will have access to identified data.

At this time, there is no plan to destroy the Patient Reported Outcome (PROs) data because of the value to this data regarding national norms for PROs for patients electing to have surgery and those electing non-surgical management of OA.

PHI including individual contact information for follow-up date collection will be destroyed after all surveys have been completed by individual patients 3 years after the completion of the study.

Published data derived from this study will consist of statistical analyses collapsed (averaged) across participants. Under no circumstances will data from individual participants be identifiable in reports or published manuscripts.

INVESTIGATOR STUDY PLAN

12.14.2021

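### Aim 3 applies use-of-Support weighting to a decision measure taken before coaching is offered, and does not name the arm contrast as its primary analysis

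*Combined protocol and SAP*

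**What the plan says.** All references are to the combined protocol and SAP.

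- **Outcome.** Section 10 lists as a primary outcome measure: "To evaluate the effect of the OA Careplan+Support on (a) decision quality using Decisional Conflict Scale", alongside pain relief and functional gain.
- **Timing.** Section 8, on the coaching session: "After the research coordinator completes the verbal consent process and the 1-month Decisional conflict assessment, s/he will then invite the patient to participate". The order is repeated where section 8 describes the Enhanced-arm interviews. The website is introduced at the end of the session, and sharing the report with the primary care provider follows it. Attendance is voluntary.
- **Who is offered Support.** Sections 8 and 11 offer coaching only at intervention sites; control patients receive the report alone.
- **Sizing.** Section 13: "Using two independent group t-tests adjusting for within surgeon clustering, the trial can detect an intervention effect". This is a contrast of arms.
- **Principle and hypothesis.** Section 13: "We will adhere to the intent-to-treat principle to analyze the trial data". The Aim 3 hypothesis on quality of care is nevertheless qualified by "for those who choose to use the Support".
- **Analyses.** For Aim 3, section 13 describes a crude arm effect, a use-weighted effect ("Because use of the SUPPORT is not randomized, we will use inverse propensity weighting approach to estimate the effects of the SUPPORT on outcomes"), an arm model that will also "adjust for propensity scores, plausible surgeon and patient factors", a pre-post comparison in carried-over surgeons, a dose-response on usage, and a three-status model for which "We will pool data from both arms in the two phases". None is labelled primary.

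**The concern.** There are three linked problems, the first being the firmest.

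1. Weighting by propensity to use Support is meant to recover the effect of use. On 1-month Decisional Conflict there is no such effect to recover, because the measure is complete before use can begin. Any user versus non-user difference that remains after weighting is residual selection, yet it would be reported as a Support effect on a listed primary outcome.
2. The arm contrast and the user contrast answer different questions and can disagree. The sizing and the intent-to-treat sentence point to the first, the wording of the hypothesis to the second. Nothing says which result decides Aim 3.
3. The adjusted arm model includes a propensity for use. Control patients cannot use Support, and the plan says neither in whom the score is fitted nor what value controls receive. Some choices are harmless; one can cost much precision or remove the effect being tested.

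**Working it through.** **Order of events (no arithmetic).** Section 8 gives this sequence in the Support arm: recruitment packet with coaching fact sheet and flyer; verbal consent; 1-month Decisional Conflict assessment; invitation to coaching; session; website; sharing with primary care. The 6- and 12-month contacts are knee or hip surveys. The post-coaching evaluation covers what was learned, confidence and understanding of the report. No second Decisional Conflict assessment is described. Use therefore cannot affect that measure. Assignment could, through the packet.

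**The plan's own figure.** Inputs from section 13: 40 surgeons, 100 patients each, ICC 0.02, 5% level (two-sided assumed), 80% power.
- Design effect = 1 + 99 × 0.02 = 2.98. Effective n per arm = 2000/2.98 = 671.
- SE = sqrt(2/671) = 0.0546 SD.
- Detectable effect with t on 38 df = 0.157 SD, or 0.157 × 20.8 = 3.27 points. The stated 0.16 SD and 3.3 points reproduce, as an arm contrast with no allowance for non-use.

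**Dilution.** Section 4 gives 3000 patients and 36 to 40 surgeons for Aim 3, so 40 × 75 is used here.
- Design effect = 1 + 74 × 0.02 = 2.48. SE = sqrt(2 × 2.48/1500) = 0.0575 SD.
- If only users benefit, arm effect = uptake × user effect. The documents give no uptake, so 15%, 30% and 50% are assumptions.

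| User effect | Arm effect (SD) | Power, 40 × 75 (noncentral t, 38 df) |
|---|---|---|
| 0.16 SD (planned size) | 0.024 / 0.048 / 0.080 | 7 / 13 / 27% |
| 0.30 SD (assumed) | 0.045 / 0.090 / 0.150 | 12 / 33 / 72% |

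For 0.30 SD, 36 surgeons with 83.3 patients each give 11/31/69%. The 54 × 100 in section 13 gives 16/47/88%. At 40 × 75, 80% power needs a user effect of 2.80 × 0.0575/uptake = 1.07, 0.54 or 0.32 SD. These powers concern pain and function; attendance cannot act on the 1-month measure.

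**Score for controls (simulation).** Settings: 40 × 75, ICC 0.02, total SD 1; one measured and one unmeasured covariate, each with outcome slope 0.3. The measured covariate and clustering are in every arm model.
- Users-only benefit of 0.30 SD at 15/30/50% uptake: the plain arm estimate is about 0.05/0.09/0.15 SD. It is identical with a score built from the baseline patient covariate and applied to both arms. With controls scored zero it is about 0.00.
- Benefit of 0.16 SD across the whole arm: zero-scored controls still return about 0.15 to 0.17 SD, so only precision is lost.
- The precision loss depends on how strongly the covariate predicts use, because a weakly varying score that is zero in controls nearly duplicates the arm indicator:

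| Use slope (log-odds per SD) | SE multiplier at 15 / 30 / 50% uptake |
|---|---|
| 1.4 | 1.1 / 1.2 / 1.4 |
| 0.7 | 1.4 / 1.7 / 2.3 |
| 0.35 | 2.3 / 2.6 / 3.6 |

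Repeat runs of 300 trials move the largest multiplier between about 3.6 and 4.0; 3.8 is a fair summary.

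**User contrast with no true effect.** Weighting within the Support arm, with a measured use slope of 0.7, gives about 0.00 SD without unmeasured confounding. It gives +0.09 SD when an unmeasured factor has a use slope of 0.3, and +0.19 to +0.20 SD at 0.7. The last exceeds the 0.16 SD the trial is sized to detect.

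**The case against.** The strongest reply is that the plan already points to the arm contrast. Section 4 compares outcomes between the two arms, section 13 sizes on arms and commits to intent-to-treat for both aims, and it reads a significant difference between arms as the sign of a Support effect. The listed estimates are not equal rivals: crude and adjusted arm effects are steps in one analysis, the pre-post and dose-response results are worded tentatively, and the pooled model is described for pain and function only. This stands. A reader might infer that six competing estimates leave the Aim 3 result open until the data are seen; the documents do not support that. What is missing is an explicit label, and a reconciliation with the user-based hypothesis and the propensity term.

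Second, the score is introduced by comparing users with non-users, which may mean within the Support arm only, and a covariate score carried to both arms does no harm. This also stands. A reader might infer that the adjusted arm estimate must be biased. That needs two unstated conditions: controls scored near zero, and benefit confined to users. The simulation used a single patient covariate, whereas the plan intends multi-level models with surgeon determinants, which are harder to carry over to control surgeons.

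Third, coaching materials reach Support-arm patients before the 1-month measure. That permits an effect of assignment on Decisional Conflict, so it would be wrong to infer that the arm contrast on it is invalid. It does not rescue an effect of use.

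**Conclusion.** The concern holds in a limited form. The timing conflict needs no assumption: use-based weighting of 1-month Decisional Conflict cannot estimate a coaching effect. The missing primary label and the undefined control score are gaps in specification, not proof of a wrong result. The sizes are illustrative, because the documents give no uptake, use slope or confounding strength. The SE multiplier of about 1.1 to 3.8 covers uptake of 15% to 50% and use slopes of 1.4 down to 0.35; a flatter slope would make it larger. It arises only if controls are scored near zero, and loss of the arm effect further requires benefit in users alone. The arm data remain sound, so this should be settled in the SAP before results are seen.

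**What to change.** 1. Name as the Aim 3 primary analysis the contrast by allocated arm in all consented Aim 3 patients, with baseline covariates and surgeon clustering, and no use-propensity weight or covariate.
2. Keep the use-weighted and dose-response analyses as exploratory, fitted within the Support arm and for 6- and 12-month pain and function only.
3. Do not apply them to 1-month Decisional Conflict. State that the arm contrast on that measure reflects assignment, including the packet materials, and not coaching received.
4. Label the pre-post and pooled two-phase models as supporting, and say that the pooled Careplan group includes Aim 2 patients.
5. State that carried-over Support surgeons had used the Careplan in Aim 2 and carried-over controls had not, and that this qualifies the primary contrast too.
6. Report uptake beside the primary result.

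The cost is SAP wording and an uptake table, with no new data. The price is dilution: power is low when uptake is low, as the 40 × 75 figures show, and the primary result will not answer the user question. Decision quality will still have no measure taken after coaching. Because Support-arm packets carry extra material before consent, consent rates by arm should be shown as well.
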